#### **SUMMARY**

This open-label, randomized parallel group clinical trial will study subcutaneous depot medroxyprogesterone acetate (DMPA sc) self-administration at two Planned Parenthood affiliates serving diverse patient populations. A total of 400 female patients (ages 15–44) requesting DMPA will be randomized to either self-administration of DMPA sc or clinic administration (usual care) in a 1:1 allocation. Subjects will be followed for one year to compare method continuation rates and patient satisfaction between arms. All subjects will receive reminders when their next injection is due. Follow-up surveys will be conducted at 6 and 12 months via secure email, phone, text messaging, or a combination to increase response rate. Adherence will be monitored by subject self-report and study outcomes will be ascertained by self-report and medical record review.

The primary study outcome is DMPA continuation at one year by self-report in both study arms. Secondary outcomes include patient-reported satisfaction with treatment; satisfaction with home use; and costs associated with contraceptive care. We hypothesize higher continuation rates among self-injection users compared to patients who receive standard care and have sufficient statistical power to detect an estimated 13% difference (80% power; one-sided  $\alpha$ =0.05; allowing for 15% loss-to-follow-up). The study will include some minors (ages 15–17) — a population at high risk of unintended pregnancy — due to limited information available from previous studies (Williams et al. 2013). The proposed trial will be substantially larger than prior studies of self-administration.

The study is funded by a private grant from the Tara Health Foundation, with additional support requested from Pfizer in the form of one-year drug supply for all randomized study participants.

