# **Objectives and Hypotheses**

The primary study objective is to compare one-year method continuation rates between patients who self-administer DMPA sc outside of the clinic setting and those who receive in-clinic administration of DMPA sc. Secondary objectives are to: confirm the feasibility and acceptability of self-injection among adult and adolescent DMPA users; compare method satisfaction rates between patients who self-administer and those who receive in-clinic injections; and compare costs associated with contraceptive care across both groups.

Primary study outcome: DMPA sc continuation at one year by self-report in both the self- and clinic administration arms.

Secondary study outcomes: Patient-reported satisfaction with treatment; satisfaction with home use; cost differentials.

Primary research question: Will allowing for self-administration of DMPA sc outside of the clinic setting result in increased method continuation rates at 6 and 12 months?

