## Secondary research questions:

- Do adult and adolescents patients report that self-administration of DMPA sc is a feasible and satisfactory alternative to clinic administration of DMPA sc?
- What are the cost-related implications of self-administration of DMPA sc compared to clinic administration for patients, providers, and payers?

Primary Hypothesis: We hypothesize higher continuation rates among self-administration users compared to patients who receive in-clinic administration.

- Independent variable: Self-administered DMPA sc versus clinic administered DMPA sc.
- Dependent variables: DMPA continuation rates at 6 and 12 months, defined as having received 3 contraceptive injections by 26 weeks post-enrollment and 4 injections by 42 weeks post-enrollment.

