#### STUDY DESIGN

This will be an open-label, randomized parallel group clinical trial to study DMPA sc self-administration at two Planned Parenthood affiliates serving diverse patient populations. A total of 400 female patients

requesting DMPA will be randomized to either self-administration of DMPA sc or clinic administration (usual care) in a 1:1 allocation. Subjects will be followed for one year to compare method continuation rates and satisfaction between arms. All subjects will receive reminders approximately two weeks before their next injection is due. Follow-up surveys will be conducted at 6 and 12 months via secure email, phone, text messaging, or a combination to increase response rate. Adherence will be monitored by subject self-report and study outcomes will be ascertained by self-report and medical record review.

We hypothesize higher continuation rates among self-administration users compared to those who receive in-clinic administration and have sufficient statistical power to detect an estimated 13% increase (80% power; one-sided  $\alpha$ =0.05, allowing for 15% loss-to-follow-up). We project a 57% one-year continuation rate among the clinic administration group based on the findings of the CHOICE Project in St. Louis, which also provided free contraception for one year and included adolescents (Peipert et al. 2011). We project a 70% continuation rate among the self-administration group based on similar studies described above (though slightly lower due to the inclusion of adolescents in our study). Given our primary research question, and that all prior studies suggest higher continuation among women self-administering DMPA, a one-tailed hypothesis test is appropriate.

The study will include minors (ages 15–17) due to exceedingly limited information available thus far, but will not oversample adolescents. The proposed trial will be substantially larger than previous studies and the first to have adequate statistical power to detect a clinically relevant and plausible difference between self-administration and usual care. To permit some assessment of generalizability of the results, we will also calculate overall DMPA continuation rates for all DMPA users at each participating health center at the end of the study period.

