### **Data Analysis**

The Principal Investigator and Data Manager have access to a secure computer with Excel, SPSS, and STATA software. Analyses will be performed on an intent-to-treat basis. We will perform descriptive analyses of demographic variables to assess the success of randomization and characterize the study population. Chi-square and t-test analyses will be used to compare proportions and mean differences between groups. The primary analysis will compare DMPA continuation rates between the intervention and control groups at 6 and 12 months. Cox proportional hazards regression analyses will be used for survival analysis. Secondary analyses will compare satisfaction scores and time/money spent on contracepting behaviors between the two groups.

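### The primary analysis names 6 and 12 months together, but the declared primary outcome and the sample size rest on 12 months alone

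*Combined protocol and SAP*

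**What the plan says.** Three statements name one year alone:

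- Summary: "The primary study outcome is DMPA continuation at one year by self-report in both study arms".
- Objectives and Hypotheses, primary objective: to "compare one-year method continuation rates between patients who self-administer DMPA sc outside of the clinic setting" and those injected in the clinic.
- Objectives and Hypotheses, primary outcome: "DMPA sc continuation at one year by self-report in both the self- and clinic administration arms".

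The sizing follows them. Study Design states: "We project a 57% one-year continuation rate among the clinic administration group". It sets 70% against this for self-administration. Number of Subjects and Statistical Power uses the same pair at 12 months.

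Three other statements, all attached to the word primary, name both times:

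- Primary research question: whether self-administration will "result in increased method continuation rates at 6 and 12 months".
- Dependent variables under the Primary Hypothesis: "DMPA continuation rates at 6 and 12 months, defined as having received 3 contraceptive injections by 26 weeks post-enrollment", followed by a separate injection count for 12 months.
- Data Analysis: "The primary analysis will compare DMPA continuation rates between the intervention and control groups at 6 and 12 months".

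Data Analysis then says: "Secondary analyses will compare satisfaction scores and time/money spent on contracepting behaviors between the two groups". The secondary outcomes in the Summary and in the Objectives are likewise limited to satisfaction and cost. Six-month continuation therefore appears only under primary labels.

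**The concern.** Data Analysis is the section that governs the tests, and it puts two comparisons inside the primary analysis when one was declared and sized. Each time point has its own binary definition, so these are two endpoints that can give different answers. Nothing says what the trial concludes if they disagree.

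The trial is open-label, and the 6-month surveys come in before the 12-month ones. Without a written rule, the weight given to each time could be settled after results are known. The Rationale says that positive findings will change the organisation's medical standards, so what counts as positive should be fixed beforehand.

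**Working it through.** **Inputs from the documents.** Continuation at 12 months 0.57 (clinic) and 0.70 (self); one-sided α = 0.05; power 80% (printed once as β = 0.80, read here as power); 1:1 allocation; 400 enrolled; 15% loss; 338 completers required. No 6-month rate, difference or power is given.

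**Step 1: reproduce the plan's figure.** The pooled-variance formula for two proportions, without continuity correction, is

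n per arm = [z(0.95)·√(2p̄(1−p̄)) + z(0.80)·√(p₁(1−p₁) + p₂(1−p₂))]² / (p₂−p₁)²

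With p̄ = (0.57 + 0.70)/2 = 0.635:

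- 2p̄(1−p̄) = 2 × 0.635 × 0.365 = 0.46355, square root 0.6808
- 0.57 × 0.43 + 0.70 × 0.30 = 0.4551, square root 0.6746
- n = (1.6449 × 0.6808 + 0.8416 × 0.6746)² / 0.13² = 168.5, so 169 per arm and 338 in total
- 338/0.85 = 397.6, so 398 enrolled, against 400 planned

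Power at 169 per arm (√169 = 13): standard errors are 0.6808/13 = 0.0524 under the null and 0.6746/13 = 0.0519 under the alternative. Φ[(0.13 − 1.6449 × 0.0524)/0.0519] = Φ(0.845) = 80.1%. The stated figure reproduces, and it spends the whole one-sided 0.05 on the 12-month comparison.

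**Step 2: if success at either time counted, each at one-sided 0.05.** With independent tests the error is 1 − 0.95² = 9.75%. This is the ceiling as long as the two tests are not negatively correlated, which is reasonable for the same women measured twice. For a correlated case, assume that every 12-month continuer is also a 6-month continuer. The correlation is then ρ = √[p₁₂(1−p₆)/(p₆(1−p₁₂))], with p₁₂ = 0.57 in both arms and p₆ assumed. The error is one minus the bivariate normal probability that both statistics fall below 1.645.

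| Assumed 6-month rate | ρ | Either-time error |
|---|---|---|
| 0.65 | 0.845 | 7.2% |
| 0.70 | 0.754 | 7.8% |
| 0.80 | 0.576 | 8.5% |
| 0.90 | 0.384 | 9.1% |

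**Step 3: if both times were required.** The trial succeeds only when the 12-month test succeeds, so error is at or below 5% and power is at or below 80.1%. The loss of power depends on the 6-month rates in both arms. The documents do not give them, so no figure can be put on it.

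**Step 4: which test decides.** Data Analysis lists chi-square tests and Cox regression without saying which settles the primary comparison, and does not repeat that the test is one-sided. An ordinary two-sided chi-square at 0.05 has the critical value of a one-sided 0.025 test: Φ[(0.13 − 1.9600 × 0.0524)/0.0519] = Φ(0.527) = 70.1% with 338 completers. The stated 80% therefore needs the one-sided test as well as the single time point.

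**The case against.** The best reply is that the intended primary endpoint is not in real doubt. The Summary and the Objectives declare one outcome, at one year; the objective agrees, and so does the sizing. Naming one time as the primary outcome already ranks the two. That stands: a reader might infer that the plan leaves 6 and 12 months wholly unranked, and the documents do not support that. What remains is that the research question, the dependent variables and the analysis section were not brought into line with the declaration.

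A reader might also infer that the trial runs at a 7% to 10% false-positive rate. It does not follow. The wording joins the times with *and*, and no section says that either one suffices. The figures in step 2 describe a rule that could be read into the gap, not one the plan states.

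Nor do the stated error and power both fail unless 12 months alone decides. Requiring both times keeps error at or below 5%. Accepting either keeps power at or above that of the 12-month test. Each alternative harms at most one of the two properties.

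Finally, the correlated figures rest on assumed 6-month rates and on assumed nesting of the two outcomes. They show scale only.

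**Conclusion.** The point holds as an inconsistency that should be fixed. The declared primary outcome, the objective and the sample size use 12 months; the primary research question, the dependent variables and the primary analysis use 6 and 12 months. No success rule or testing order joins them.

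The size of the problem is conditional. Under an either-time reading, error would be at most 9.75% (tests not negatively correlated), or about 7% to 9% for assumed 6-month rates of 65% to 90% with 12-month continuers nested in 6-month continuers. Under a both-times reading, error is controlled and power is capped at 80.1%, with a shortfall that cannot be quantified. Under the 12-month reading that most of the text favours, the stated figures hold, provided the deciding test is the one-sided comparison of proportions.

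**What to change.** - In Objectives and Hypotheses, in the dependent variables under the Primary Hypothesis, and in Data Analysis, name 12-month continuation as the single primary endpoint.
- In Data Analysis, state that it is decided by a one-sided 0.05 comparison of two proportions, as Study Design and Number of Subjects and Statistical Power assume, and give the Cox model a supporting role.
- Move 6-month continuation to the secondary outcomes and secondary analyses. If a formal 6-month claim is wanted, test it only if the 12-month test succeeds.

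The cost is wording. N stays at 400, and the stated 80% power holds on the condition that the one-sided test decides. The downside is that success cannot be claimed on 6 months alone. Keeping two primary endpoints with an equal split (one-sided 0.025 each) would be dearer: 12-month power falls to 70.1% with 338 completers, and restoring 80% needs 215 per arm, or 430 completers and 430/0.85 = 505.9, so 506 enrolled.

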#### **Number of Subjects and Statistical Power**

The study sites will enroll a combined total N of 400 women. Individuals will be randomized to self-administration or clinic administration with a 1:1 allocation, such that 200 women will be randomized to self-injection, and 200 women to clinic administration. A 15% loss to follow-up rate will yield completed surveys from approximately 340 participants. Based on previous studies, we hypothesize greater continuation rates among self-injection users compared to patients who receive standard care and have sufficient statistical power to detect a difference of 13% or greater. While we will ask subjects about unintended pregnancies, given the high efficacy of DMPA, we will not have statistical power detect a difference between groups.

Given the primary study hypothesis that increased accessibility to DMPA through self-administration will result in higher method continuation rates and the results of prior studies, we estimate that the intervention group will have a 70% continuation rate at 12 months and the control group a 57% continuation rate. With a one-sided  $\alpha$ =0.05 and a  $\beta$ =0.80 and accounting for an approximately 15% dropout rate, completed follow-up from 338 subjects will be sufficient to detect the hypothesized difference. The study is not designed to detect statistically significant differences between adolescents and adults, or between method initiators and continuers.

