#### **Previous Similar Studies**

Prior studies show that DMPA self-injection is effective, feasible, and acceptable to patients. Most recently, Beasley et al. (2014) conducted a randomized trial with 137 women to evaluate the feasibility, acceptability, and continuation of self-administration of DMPA sc versus clinical administration, and to confirm the therapeutic effect using trough serum levels. They found that 90 out of 91 women randomized to the self-administration group were able to correctly self-inject. Continuation rates were somewhat higher in the self-administration group (71% vs. 63%); however, this difference was not statistically significant (p=0.47) and the study did not have adequate statistical power to detect a difference of this magnitude (i.e., 8%). All of the women who reported continuous use of DMPA had serum levels in the therapeutic range, confirming the ability of women to learn self-administration, continue it successfully at home, and reliably self-report such use. This study required repeated visits in both groups to assess serum levels and therefore involved significant intervention with both groups, potentially attenuating the difference between groups.

A non-randomized study of 120 women by Cameron et al. (2012) found that 80% of self-injections were given on time, and that no injections were given beyond the acceptable 14-week interval. The authors also found that continuation rates were higher in the self-administration group than the clinic

administration group (88% vs. 72%); however, this difference was not statistically significant and again the study did not have statistical power to detect such a difference. Cameron et al. found that the majority of women who wanted to use Depo at home were able to do so; however, 20% experienced some difficulty with one or more of the self-injections due to either resistance to the medication passing through the needle (17%) or the needle detaching from the syringe (2%).

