### Randomization and Assignment

Subjects who consent to participate will then be randomized to self-administration or standard clinic administration in a 1:1 allocation as follows. Before the study begins, the sequence for 1:1 group allocation will be predetermined stratified by study site. Separate randomization sequences will be generated for each site using randomly permuted number blocks.

Group assignments will be placed in sealed opaque envelopes and will be maintained by the Research Coordinator. The envelopes will be opened by the Research Coordinator or approved representative only after participant enrollment and informed consent. Study staff will complete and sign a Randomization Form for each randomized subject (See Appendix).

Crossover will be permitted from the self-administration arm to the clinic administration arm only. Any subject crossover will be documented by the Research Coordinator or approved representative with the subjects' ID number to permit later assessment of crossover and ITT analyses.

Due to the nature of the study, no blinding will be used.

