## **Study Procedures**

Once enrolled, all participants will be seen by a clinician. Based on study assignment, subjects will either be taught to self-inject or will be administered DMPA by qualified clinic personnel. Nurses who dispense DMPA sc (regardless of study arm) will record the name of each subject receiving the medication, her chart number, and the lot number of the medication distributed to the patient on a Study Drug Distribution Log to be maintained in the pharmacy.

Subjects who are randomized to self-administration will be taught self-administration by a clinic nurse (or other qualified personnel) following an instructions sheet based on the drug packaging insert. If willing, subjects will then self-administer DMPA sc under nurse supervision. Subjects who are able to correctly self-administer DMPA sc as assessed by the supervising nurse and who are interested in continued home self-administration will then be provided medication (3 doses of DMPA sc), a self-administration kit (includes alcohol swabs, cotton pads, bandages, mini sharps disposal container), and instructions to do so for the subsequent 3 injections along with a small calendar showing the appropriate dates for injection. The calendar will also indicate when the subject will be asked to complete each of the 2 follow-up surveys.

Subjects who are uninterested in self-administration either after the educational session or after correctly self-administering medication in the office will be permitted to crossover to the clinic administration group and remain in the study. They will be re-assigned to the clinic administration group and be followed accordingly. Subjects will not be told ahead of time that they can opt out of their randomization assignment and remain in the study to discourage enrollment of subjects who are not actually willing to be in the self-administration group.

Subjects new to DMPA will be started using the QuickStart protocol (per Planned Parenthood routine practice) and will be instructed to perform a provided pregnancy test in four weeks and report the result to clinic to be documented by the Research Coordinator in the subject correspondence log. Subjects who did not provide the result of the pregnancy test will be contacted by study staff to be documented in the correspondence log.

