## **Follow-Up Procedures**

Subjects will either return to the enrollment clinic or perform self-injection every 12–14 weeks, depending on study arm. The appropriate date for injection will be indicated on the subject's instructions for injection/calendar. All subjects (both arms) will receive reminder emails and/or text messages two weeks *before* their next injection is due. Reminders will be generated by PPFA investigators using the secure Qualtrics electronic survey platform which enables programmable email and text message communications.

If a subject is uncertain if she was able to administer the entire dose of DMPA she should return to the enrollment clinic and have a complete dose administered. The event will be recorded and reported to the Pfizer Quality Complaints department. These subjects may continue to receive injections at the enrollment clinic or return to self-administration; this will be documented by the site Research Coordinator.

Subjects who are uncomfortable with self-injection at any point in the study may return to the enrollment clinic to receive their injection per usual clinic protocol (i.e. study arm crossover to usual care will be permitted and tracked). They will be asked to complete all surveys and follow-up activities and be included in the clinic administration group. Subjects should continue to complete all surveys regardless of the location at which she receives her injection.

Crossover will be permitted from the self-administration arm to the clinic administration arm only. Any subject crossover will be documented by the Research Coordinator with the subjects' ID number to permit later assessment of crossover and ITT analyses.

The Research Coordinator will provide the Principal Investigator with a list of subjects enrolled each month so that PPFA investigators can complete the appropriate follow up. Approximately two weeks after subjects' target injection dates, follow-up surveys will be emailed by PPFA investigators to all participants. If no survey is completed by 16 weeks after previous injection, study staff will contact the subject twice and at her alternate contact to remind them to complete the survey whether they administered DMPA or not.

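### The stated 80% power allows for loss to follow-up but not for the one-way crossover the protocol permits under intent to treat; the assumption behind the 70% self-administration rate should be stated

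*Combined protocol and SAP*

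**What the plan says.** The Summary, Study Design, and Number of Subjects and Statistical Power sections all claim 80% power at one-sided 0.05 to detect a 13-point difference, 70% against 57%, with 200 women per arm and 15% loss to follow-up. The last of these concludes: "accounting for an approximately 15% dropout rate, completed follow-up from 338 subjects will be sufficient to detect the hypothesized difference". None of the three mentions crossover.

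Study Design takes the 57% from a cohort that also received free contraception. It takes the 70% from the self-injection studies, "though slightly lower due to the inclusion of adolescents in our study". No other reason for the reduction is given.

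Crossover is part of the design. Randomization and Assignment states: "Crossover will be permitted from the self-administration arm to the clinic administration arm only". It can happen at the first visit: "Subjects who are uninterested in self-administration either after the educational session or after correctly self-administering medication in the office will be permitted to crossover". Follow-Up Procedures extends it to any woman who becomes uncomfortable with self-injection at any point. Data Analysis states: "Analyses will be performed on an intent-to-treat basis".

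Two further statements bear on how crossovers are handled. Study Procedures says that women who cross over at the first visit are moved to the clinic group and followed as such, and Follow-Up Procedures says that later crossovers are counted in that group. Follow-Up Procedures also says, of women given a clinic dose because they were unsure that a full dose went in: "These subjects may continue to receive injections at the enrollment clinic or return to self-administration".

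**The concern.** Under intent to treat, a woman assigned to self-administration who moves to the clinic stays in the self-administration arm. If she then continues at about the clinic rate, she pulls that arm's rate towards 57%. Movement is allowed in one direction only, so nothing offsets this. The contrast shrinks even when intent to treat is applied correctly.

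The sample size meets 80% almost exactly at the full 13 points, so it holds no reserve for such dilution. At stake is how a null result would be read: reduced power from dilution could be taken as evidence that self-administration does not help. Study Design presents the trial as the first with adequate power for this question, so the condition attached to that power should be visible.

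**Working it through.** **Inputs.** From Number of Subjects and Statistical Power: clinic rate p1 = 0.57, self-administration rate p2 = 0.70, one-sided alpha 0.05, 338 completers (169 per arm). That section labels 0.80 as beta; it is read here as power, as in the Summary and Study Design. Normal quantiles: 1.645 and 0.842.

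**Step 1: reproduce the plan's figure.** Pooled-variance formula for two proportions, no continuity correction:

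n per arm = [1.645 × √(2p̄(1−p̄)) + 0.842 × √(p1(1−p1) + p2(1−p2))]² / (p2−p1)²

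With p̄ = 0.635: [1.645 × 0.6808 + 0.842 × 0.6746]² / 0.13² = 168.5, rounded up to 169, or 338 in total. Then 338 / 0.85 = 398, about 400. The plan's figure is confirmed.

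Power with 169 per arm = Φ{[(p2−p1) − 1.645 × √(2p̄(1−p̄)/n)] / √[(p1(1−p1) + p2(1−p2))/n]} = Φ[(0.13 − 1.645 × 0.05237) / 0.05189] = Φ(0.845) = 80.1%.

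**Step 2: allow for crossover.** Let c be the share of the self-administration arm that crosses over. The documents give no value for c. Two assumptions are made: 70% is the rate among women who self-inject, and crossovers continue at 57%. The arm's intent-to-treat rate is then 0.70 − c × 0.13.

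For c = 10%: 0.70 − 0.013 = 0.687, a difference of 0.117, and power = Φ[(0.117 − 1.645 × 0.05257) / 0.05218] = Φ(0.585) = 72.1%.

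| Crossover c | Self-arm rate | Difference (points) | Power, 169 per arm |
|---|---|---|---|
| 0% | 70.0% | 13.0 | 80.1% |
| 1.1% (1/91) | 69.9% | 12.9 | 79.3% |
| 5% | 69.35% | 12.35 | 76.3% |
| 10% | 68.7% | 11.7 | 72.1% |
| 15% | 68.05% | 11.05 | 67.6% |
| 20% | 67.4% | 10.4 | 62.9% |

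The 1/91 row uses the one woman of 91 in the cited randomized trial (Previous Similar Studies) who was not able to self-inject correctly. It is a reference point for inability, not a crossover rate.

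**Step 3: vary the assumptions.**
- If crossovers keep half the benefit, the effective dilution is c/2: power is 76.3% at 10% crossover and 72.1% at 20%.
- If all 400 women are analysed (200 per arm), power is 78.3% at 10% and 69.3% at 20%.
- If 70% already describes everyone randomized to self-administration, there is no loss and power stays at 80.1%.

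**The case against.** The strongest reply is that 70% is stated for the intervention group, an arm-level rate. Power is 80% whenever that randomized arm reaches 70%, whatever the crossover. A reader might infer that the trial has 80% power only if nobody crosses over; that does not follow. The 71% from the cited randomized trial may itself be an as-randomized rate, in which case subtracting for crossover would count dilution twice. This stands in part: the text does not say which rate is meant, and the only reduction it explains is for adolescents. That ambiguity is what needs resolving.

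A second reply is that crossover may be low. Eligibility requires willingness to attempt self-injection and to be randomized, Informed Consent says that patients with no interest in learning the procedure should not enrol, and women are not told beforehand that they can switch. This also stands. A reader might take the non-randomized study in which "20% experienced some difficulty with one or more of the self-injections" as evidence that crossover will be common, but that figure counts problems such as resistance in the needle, not women who switched. Nor does 90 of 91 able to self-inject show that crossover will be rare, because the protocol also allows switching for lack of interest or discomfort.

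Third, late crossovers may have self-injected several doses and kept part of the benefit. This stands, and it makes the main table the less favourable case.

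Finally, a reader might infer from the regrouping statements that the trial will be analysed as treated. The documents do not support that: they commit to intent to treat and document crossover partly for that purpose. Follow-Up Procedures also already provides for tracking crossover and documenting returns to self-injection, so the data gap is small.

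**Conclusion.** The point holds as one of undisclosed planning assumptions. There is no arithmetic error: 338 is right for 70% against 57%. What is missing is a statement that this power makes no allowance for crossover that the design itself permits. Under the assumptions in Step 2, power falls from 80% to about 79%, 76%, 72% and 63% at 1%, 5%, 10% and 20% crossover. These rates are illustrative, and the documents do not support a forecast that any of them will occur. The loss is smaller with late crossover that keeps some benefit, and absent if 70% was meant as the as-randomized rate. The validity of the intent-to-treat comparison is not in question, provided crossovers are analysed in the arm to which they were randomized.

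**What to change.** Leave N unchanged; without a crossover rate there is no firm basis for a new one.

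1. In the Summary, Study Design, and Number of Subjects and Statistical Power sections, state that 80% power requires a 70% continuation rate among all women randomized to self-administration and that no allowance is made for crossover. Give the illustrative range (79%, 76%, 72% and 63% at 1%, 5%, 10% and 20%) with its assumption.
2. Reconcile Study Procedures and Follow-Up Procedures, which place crossovers in the clinic group and allow some women to return to self-injection, with the one-way rule in Randomization and Assignment and with analysis as randomized in Data Analysis.
3. Optionally, add one supportive estimate beside intent to treat: the intent-to-treat difference divided by the proportion not crossing over at the first visit, with its confidence interval. In the 10% illustration, with all crossover at the first visit, this is 11.7 / 0.90 = 13.0 points. It should be limited to first-visit crossover and state its assumption that assignment has no effect on continuation in those women. It should not be extended to women who self-inject at home and later switch or return, because that assumption fails for them and the estimate can overstate the effect. It aids interpretation but does not restore power.

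The cost is wording in a few sections and, if wanted, one extra estimate from crossover data the protocol already plans to record. The sponsor would have to accept a stated power that may fall below 80%.
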